APPENDIX A

MUPRE	MUPOST	Difference Array
1	9	8
2	8	6
4	13	9
5	16	11
6	15	9
8	19	11
14	18	4

Average Difference per person (for T test USE):

$= \text{Average}(\text{Differences})_{\text{per person}}$

$$= \frac{(8) + (6) + (9) + (11) + (9) + (11) + (4)}{7}$$

$$= 8.286$$

Supplementary Figure 1: Pre/Post Difference

In order to compare the reorganization in recruitment, the difference in order of recruitment was calculated and put into an array. This difference array was calculated for each person, and an average difference in recruitment per person was analysed using a t-test. The reason for having an average per person was to avoid any bias by having multiple data points per person that correspond to different motor units. Assumptions of normality and homogeneity of variances were verified from the Shapiro- Wilk test ($p=0.187$) and Levenes Statistic($p=0.081$), therefore a t-test can be used.

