2.2.3 Electromyograms recordings after application of intervention

To confirm the presence of central sensitization, brush allodynia will be used to detect mechanical allodynia outside the region of the primary nociception – region of topical placement – which is the region of secondary allodynia [25]. Upon confirmation of central sensitization, in participants with application of topical capsaicin, participants will be entered into the experimental arm of the study.

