2.4 Statistical Methods

2.4.1 Surface EMG

An independent samples t-test will be performed on the difference in recruitment position using treatment as the factor for the trapezius muscle. In particular, the statistical test will compare

post-pre capsaicin recruitment differences against post-pre placebo recruitment differences. The average difference in recruitment order will be used to avoid bias of having multiple data points per participant that correspond to different motor units.

2.4.2 *Intramuscular EMG*

From the intramuscular EMG algorithm mentioned in section 2.3.2, the resultant matrices will be the variances for the pre-recording motor unit trains. The statistical model used will assess the difference between the pre- and post- recording motor units for each capsaicin and placebo as well as a between group comparison (Post-Pre capsaicin motor unit variance vs. Post-Pre placebo motor unit variance). These analyses would provide insight into our hypothesis that sensitization induced by capsaicin effects upon the motor unit characteristics. Either an independent samples t-test or a Kruskal-Wallis H test will be performed, depending on how many participants' pre and post motor units match up.

3 Sample Size Calculation

The minimum sample size required per group to detect whether a significant difference exists between two means for one dependent variable was calculated with a confidence level of 95%, a 80% statistical power level and 5% error. A mean detectable difference of 5 for the dependent variable, mean motor unit recruitment change, and an estimated standard deviation of 3 was used. The estimated sample size was 7 people per group; however, considering a 20% drop out rate, the suggested sample size was 9 people per group. This analysis was completed using PASS Software, version 15.

4 Conclusions

This may provide some insights for the neurophysiological influence of central sensitization on changes in efferent responses and movement patterns that occur in patients with persistent pain. However, the clinical implication of this experimental findings on the movement properties needs to be further investigated.

5 References

- [1] IASP, "Classification of chronic pain: descriptions of chronic pain syndromes and definitions of pain terms," *Pain* 1994; Suppl 3: 1–226.
- [2] I. o. Medicine, Relieving Pain in America: A Blueprint for Transforming Prevention, Care, Education, and Research, Washington,DC: The National Academies Press, 2011.

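### Non-significant Shapiro-Wilk and Levene tests cannot justify a pooled t-test at this sample size; the plan should name the Welch t-test outright

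*Combined protocol and SAP*

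**What the plan says.** Section 2.4.1 sets the surface EMG comparison: "An independent samples t-test will be performed on the difference in recruitment position using treatment as the factor for the trapezius muscle". Each participant contributes one value, the mean change in recruitment order over matched motor units. The section names neither the Student (pooled) nor the Welch form, and it gives no alternative test for this endpoint.

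Appendix A, under Supplementary Figure 1, adds the justification: "Assumptions of normality and homogeneity of variances were verified from the Shapiro- Wilk test", with p=0.187, and from Levene's test, with p=0.081; "therefore a t-test can be used". Equal variances are a requirement of the pooled test only, so this wording points to the pooled form. That is an inference.

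Section 3 sizes the trial on this variable, with one SD for both groups: "A mean detectable difference of 5 for the dependent variable, mean motor unit recruitment change", and "an estimated standard deviation of 3 was used". It arrives at 7 per group, or 9 after 20% dropout.

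Three places bear on arm sizes. The Abstract gives 20 participants, section 2.1 gives 23, and neither states an allocation ratio. Section 2.2.3 says: "Upon confirmation of central sensitization, in participants with application of topical capsaicin, participants will be entered into the experimental arm of the study". No matching condition is stated for placebo.

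**The concern.** A non-significant assumption test counts as support only if it would probably have detected a violation that matters. With 7 to 10 people per arm, Levene's test usually would not. A p-value of 0.081 is therefore weak ground for assuming equal variances.

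This matters because the pooled t-test is robust to unequal variances when the arms are equal in size, but not when they differ. If the smaller arm is the more variable one, the pooled standard error is too small and the test rejects too often. If the larger arm is the more variable one, the test loses power. The comparison affected is the only one the trial is sized for. Unequal analysed arms are plausible here: entry to the capsaicin arm depends on confirmed sensitization, and one of the two stated totals is odd.

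**Working it through.** **Inputs.** From section 3: difference 5, common SD 3, 80% power, 5% error (two-sided assumed, since sidedness is not stated), 7 per group, 9 with dropout. From the Abstract and section 2.1: total 20 or 23. Assumptions not in the documents: normal data, an SD ratio of 1.5, 2 or 3 between arms, and the unequal splits listed below.

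**The plan's own figure.** For the pooled t-test, the noncentrality is (5/3)·√(n/2) with 2n−2 degrees of freedom. At n=7 it is 1.667 × √3.5 = 3.118 with 12 df, and power is 81.6%. At n=6 power is 74.0%. So 7 per group is reproduced. Dropout: 7/0.8 = 8.75, rounded up to 9.

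**Power of the pre-tests (simulation).** Mean-centred Levene, 7 to 10 per arm:
- SD ratio 1.5: 14-19%
- SD ratio 2: 29-42% (37% at 9/9, 42% at 10/10)
- SD ratio 3: 55-76%

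The median-centred version has less: 4-13%, 11-31% and 29-64%. With 9 or 10 per arm, a Levene p near 0.081 goes with a median observed SD ratio of 1.7-1.75 when the true SDs are equal, and of 2.0-2.1 when the true ratio is 2. The reported p-value fits either case.

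For Shapiro-Wilk at n=7-10, power is 28-44% against exponential data and 14-18% against t with 3 df. At a pooled n of 18-20 it is 79-83% and 31-34%. The appendix does not say which sample was tested.

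**Why arm sizes matter.** Take SD 2 in an arm of 7 and SD 1 in an arm of 10.
- True variance of the mean difference: 4/7 + 1/10 = 0.671.
- Expected pooled variance: (6×4 + 9×1)/15 = 2.2, which gives 2.2 × (1/7 + 1/10) = 0.534.
- Ratio: 0.534/0.671 = 0.80. Its square root is 0.89, so the standard error is about 11% too small.

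Reversed, with SD 2 in the arm of 10: the true value is 1/7 + 4/10 = 0.543, the pooled value is (6×1 + 9×4)/15 × 0.243 = 0.680, and the ratio is 1.25, so the test is conservative. At 10/10 both values are 0.5 and the bias vanishes.

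**Type I error of the pooled test, SD ratio 2, larger SD in the smaller arm.** Simulation, 60,000 to 400,000 trials per scenario; ranges show the spread over repeated runs.

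| Arms | Pooled error |
|---|---|
| 9/9 and 10/10 | 5.4-5.6% |
| 11/12 | 6.0-6.2% |
| 8/10 | 7.2-7.3% |
| 7/9 | 7.4-7.7% |
| 7/10 | 8.3-8.4% |
| 8/12 | 8.7-8.9% |
| 6/10 | 9.7-9.8% |
| 7/13 | 10.7-10.8% |

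Sensitivity to the assumed SD ratio (1.5 / 2 / 3): 7/9 gives 6.3 / 7.4 / 9.1%, and 8/12 gives 7.1 / 8.7 / 11.0%. With the larger SD in the larger arm and a ratio of 2, the error is 2.2-4.8%.

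Passing Levene gives no protection. Among simulated trials that pass, at SD ratio 2 with the larger SD in the smaller arm, pooled error is 8.9% at 7/9, 10.6% at 8/12 and 12.8% at 7/13. Among those with a Levene p near 0.081 it is 6.4% at 7/9 and 8.6% at 8/12.

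**Welch.** Type I error is 4.7-5.3% for splits from 7/7 to 8/12 at SD ratios 1.5 to 3, and 5.2-5.3% at 7/10, 6/10 and 7/13 with a ratio of 2. Power when variances are equal (difference 5, SD 3), pooled to Welch:
- Equal arms: 81.5 to 80.6% at 7/7; 91.2 to 90.8% at 9/9; 94.0 to 93.9% at 10/10.
- Unequal arms: 86.7 to 85.7% at 7/9; 88.4 to 87.1% at 7/10; 93.2 to 92.4% at 8/12; 85.0 to 82.3% at 6/10; 91.9 to 89.9% at 7/13.

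**The case against.** The planned arms are equal, and with equal arms the pooled test is nearly correct whatever the SDs. That stands, and it keeps the severity modest.

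A reader might infer that unequal arms alone push the error to 8-11%. They do not. That figure needs a clearly smaller arm and about twice the SD in that same arm, and the documents give neither. At 11/12, the natural split of 23, the error is about 6% even with a two-fold SD ratio.

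A reader might also infer that the capsaicin arm will be both smaller and more variable. The documents do not support a direction. Keeping only participants with confirmed sensitization could make that arm more homogeneous, which would make the test conservative. Levene's p-value does not say which arm varied more.

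Nor do the documents describe a rule that picks the test from the outcome data. Section 2.4.1 states the t-test without a condition: "An independent samples t-test will be performed on the difference in recruitment position". The only either/or choice of test is for intramuscular EMG and depends on how many motor units match. Error rates for a switch to Welch after a significant Levene test would describe a procedure that is not in the plan.

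Finally, it would be too strong to say that Shapiro-Wilk has little power in general. On the pooled sample it has good power against strong skewness.

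What survives is narrower: the stated justification does not establish equal variances, and the form of the test is left to inference.

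**Conclusion.** The point holds as a modest one. Appendix A takes non-significance as verification, and Levene's test at 9 to 10 per arm would miss a two-fold SD difference about 60% of the time. Whether this harms the trial cannot be settled from the documents.

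Under an assumed SD ratio of 2 with normal data and the larger SD in the smaller arm, pooled type I error runs from about 5.5% with equal arms, through 6-8% at mild imbalance, to 8-11% at 7/10, 8/12, 6/10 or 7/13. In the reverse direction it is about 2-5%. The conclusion also rests on reading the unnamed t-test as the pooled one. If Welch was intended, only the wording needs to change. Welch would not repair the selection of capsaicin participants after randomisation, which is a separate matter.

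**What to change.** In section 2.4.1 and Appendix A, name the Welch t-test, with its 95% CI for the difference in means, as the test of the per-participant recruitment difference, without any assumption pre-test. Delete the statement that the pre-tests justify the t-test. An exact permutation or rank test could be added as a sensitivity analysis.

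The appendix is written in the past tense and reports p-values. If the pooled analysis has already been run, report both results and disclose the change.

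The cost is a wording change and one software option. In power it is about 0.2-1 point with equal arms and 1-3 points at the more unequal splits. The lowest Welch power among the splits above is 80.6%, at 7/7, so the stated 80% is kept.
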